## STATEMENT OF COMPLIANCE

The trial will be conducted in accordance with International Conference on Harmonisation Good Clinical Practice (ICH GCP), applicable United States (US) Code of Federal Regulations (CFR), and the <specify NIH Institute or Center (IC) > Terms and Conditions of Award. The Principal Investigator will assure that no deviation from, or changes to the protocol will take place without prior agreement from the Investigational New Drug (IND) or Investigational Device Exemption (IDE) sponsor, funding agency and documented approval from the Institutional Review Board (IRB), except where necessary to eliminate an immediate hazard(s) to the trial participants. All personnel involved in the conduct of this study have completed Human Subjects Protection and ICH GCP Training.

The protocol, informed consent form(s), recruitment materials, and all participant materials will be submitted to the IRB for review and approval. Approval of both the protocol and the consent form must be obtained before any participant is enrolled. Any amendment to the protocol will require review and approval by the IRB before the changes are implemented to the study. All changes to the consent form will be IRB approved; a determination will be made regarding whether a new consent needs to be obtained from participants who provided consent, using a previously approved consent form.

## LIST OF ABBREVIATIONS

ADT	Androgen Deprivation Therapy
AE	Adverse Event
AR	Androgen Receptor
CFR	Code of Federal Regulations
CrCl	Creatinine clearance
CRF	Case Report Form
CRPC	Castration Resistant Prostate Cancer
CTCAE	Common Terminology Criteria for Adverse Events
CYP	Cytochrome P450
DSMB	Data Safety Monitoring Board
DSMP	Data Safety Monitoring Plan
ECG	Electrocardiogram
ECOG	Eastern Cooperative Oncology Group
FDA	Food and Drug Administration
GCP	Good Clinical Practice
HIPAA	Health Insurance Portability and Accountability Act of 1996
HRBFA	Human Research Billing Analysis Form
HUD	Humanitarian Use Device
ICF	Informed Consent Form
IDE	Investigational Device Exemption
IND	Investigational New Drug
IRB	Institutional Review Board
PCWG3	Prostate cancer working group 3
PFS	Progression-free survival
PHI	Protected Health Information
PI	Principal Investigator
PO	Per os (by mouth)
RECIST	Response Evaluation Criteria In Solid Tumors
REDCap	Research Electronic Data Capture
rPFS	Radiographic progression-free survival
SAE	Serious Adverse Event
SUSAR	Suspected Unexpected Serious Adverse Reaction
UAP	Unanticipated Problem
WCM	Weill Cornell Medicine

[figure not shown]

## 1. PROTOCOL SUMMARY

Full Title	Open Label Phase II Trial of Cabozantinib in Patients with Metastatic Castrate Resistant Prostate Cancer (mCRPC) and Known Amplifications or Activating Mutations in Gene Targets of Cabozantinib or Liver Metastases who have Received Prior Anti-Androgen Therapy
Short Title	Cabozantinib for mCRPC
Clinical Phase	Phase 2
Principal Investigator	[name]
Sample Size	N = 30
Accrual Ceiling	Enroll up to 30 subjects and screen up to 100 subjects
Study Population	Men with CRPC who have progressed on a second-line anti-androgen therapy
Accrual Period	24 months
Study Design	
This is a phase II non-randomized, open label trial designed to evaluate treatment response and survival of patients with mCRPC who harbor evidence of increased signaling (via evidence of DNA amplification or RNA overexpression) of the targets of cabozantinib (MET, KIT, RET, VEGFR-1 (FLT1), VEGFR-2 (KDR), VEGFR-3 (FLT4), FLT3, AXL, TRKB, and TIE2) or who have or liver metastases.
 
All patients will receive cabozantinib at 40 mg/day. Dose reduction (from 40 to 20 mg and to 20 mg every other day) or interruptions of treatment will be allowed for unacceptable adverse events (AEs).

Study Duration	Approximately 12 months after enrollment, then patients will shift to long-term follow up
Study Agent	Cabozantinib, 40 mg PO daily
Primary Objective	To assess the radiographic response proportion of cabozantinib in patients with metastatic CRPC who have progressed on an androgen receptor signalinginhibitor whose tumor possess a molecular abnormality that is targeted by cabozantinib or who have liver metastases
Secondary Objectives	
 
• To assess PSA decline by PCWG3
 
• To measure overall survival (OS)
 

Exploratory Objectives	
 
• To explore prognostic and/or predictive biomarkers of cabozantinib in whole blood, plasma and tumor samples: 
 
○ To evaluate for and measure changes in targeted genes found in cell-free DNA at baseline, in response to treatment, and at the time of disease progression
 
○ To explore the effects of cabozantinib on
 
 
 

	
tumor immune microenvironment response through on-treatment biopsy, ideally of same pre-treatment site, and collection of plasma for analysis
 
 
○ To explore any relationship between baseline and on-treatment tumor genomic alterations (such as mutations, translocations, messenger ribonucleic acid [mRNA], protein expression and localization) with any observed antitumor activity
 

Endpoints	
Radiographic progression free survival, response rate (radiographic RR, ≥50% PSA response rate, overall survival, and adverse event rate

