#### *MET and VEGFR2 signaling in prostate cancer*

Beyond AR signaling, PC growth can be affected through targeting the MET and VEGFR2 signaling

pathways. The receptor tyrosine kinase MET plays important roles in cell motility, proliferation, and survival, and has been shown to be a key factor in tumor angiogenesis, invasiveness, and metastasis. Prominent expression of MET has been observed in primary and metastatic PCs [15, 16] with evidence for higher levels of expression in bone metastases compared to lymph node metastases or primary tumors [17, 18]. Overexpression of hepatocyte growth factor (HGF), the ligand for MET, has also been observed in PC [19], and increased plasma levels of HGF in CRPC are associated with decreased overall survival [20].

Data from preclinical studies suggest that both HGF and MET are regulated by the AR signaling pathway in prostatic tissue [15, 21, 22]. MET expression increases substantially in androgen-sensitive tumor cells after androgen withdrawal [15, 21, 22]. Administration of a MET kinase inhibitor after castration reduced tumor cell proliferation in a preclinical model of CRPC [21]. These observations indicate that upregulation of MET signaling may be associated with and contribute to the emergence of resistance to androgen suppression in PC.

Vascular endothelial growth factor (VEGF) and its receptors are key mediators in the process of tumor neoangiogenesis, invasion, and metastasis [23]. In PC, elevated VEGF in either plasma or urine is associated with shorter overall survival [24, 25]. VEGF may also play a role in activating the MET pathway in tumor cells by binding to neuropilin-1, which is frequently upregulated in PC and appears to activate MET in a co-receptor complex [18]. Agents targeting the VEGF signaling pathway have demonstrated activity in some patients with CRPC [26].

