### 4.2 Inclusion Criteria

1. Age >18 years.
2. Documented histological or cytological diagnosis of prostate carcinoma.
3. Evidence of metastatic PC on imaging (bone scan and/or CT/MRI scan)
  - a. Patients with liver metastases must have biopsy proven evidence of metastatic prostate cancer in the liver
4. Agree to undergo a biopsy of at least one metastatic site or primary prostate prior to beginning therapy. Adequate archival metastatic tissue can be used if available in lieu of a biopsy if done when patient had CRPC and within 6 months the start of treatment.
5. Agree to undergo a biopsy of at least one metastatic site or primary prostate after 3 weeks of therapy (biopsy must be between day 21 and day 24 of treatment). Re-biopsy of same pre-treatment biopsy soft tissue site especially liver metastases is preferred.
6. Serum testosterone level less than 50 ng/dL. Subjects without prior orchiectomy must be currently taking and willing to continue luteinizing hormone-releasing hormone (LHRH) analogue (agonist or antagonist) therapy until permanent discontinuation of study treatment.
7. Documented progressive metastatic CRPC based on at least one of the following criteria:
  - a. PSA progression according to Prostate Cancer Working Group 3 (PCWG3) criteria
  - b. Objective radiographic progression, according to PCWG3 criteria
8. ECOG performance status of 0-1
9. Recovery to baseline or  $\leq$  Grade 1 CTCAE v4 from toxicities related to any prior treatments, unless specified below or AE(s) are clinically nonsignificant and/or stable on supportive therapy.
10. Adequate organ and marrow function, based upon meeting all of the following laboratory criteria **within 14 days before first dose of study treatment**:
  - a. Absolute neutrophil count (ANC)  $\geq 1500/\text{mm}^3$  ( $\geq 1.5 \text{ GI/L}$ ) without granulocyte colony-stimulating factor support
  - b. White blood cell count  $\geq 2500/\text{mm}^3$  ( $\geq 2.5 \text{ GI/L}$ )
  - c. Platelets  $\geq 100,000/\text{mm}^3$  ( $\geq 100 \text{ GI/L}$ ) without transfusion.
  - d. Hemoglobin  $\geq 9 \text{ g/dL}$  ( $\geq 90 \text{ g/L}$ )
  - e. Total bilirubin  $\leq 1.5 \times \text{ULN}$  (for subjects with Gilbert's disease  $\leq 3 \times \text{ULN}$ )
  - f. Serum albumin  $\geq 2.8 \text{ g/dL}$
  - g. Serum creatinine  $\leq 2.0 \times \text{ULN}$  or calculated creatinine clearance  $\geq 30 \text{ mL/min}$  ( $\geq 0.5 \text{ mL/sec}$ ) using the Cockcroft-Gault equation:

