## **12.4 Analysis of Exploratory Endpoints**

Data generated will include IHC scores for targets of cabozantinib, scores for immune cell infiltrate, whole exome sequencing (WES), targeted DNA sequencing, and RNA-Seq for expression. Measures with significant changes from baseline will be determined using the appropriate two-sample test: either a paired t-test or Wilcoxon signed rank test for continuous measures and a chi-square test for categorical variables. The Benjamini-Hochberg procedure will be used to control the false discovery rate for the genomic measurements (DNA, RNA Seq). If the variables are ordinal, an analysis will be done for the proportion of changes that were "positive", "negative", or "no change". An assessment of differences between groups (*e.g.* patients with and without tumor response) will be evaluated with a two-sample t-test or Wilcoxon rank sum test, whichever is most appropriate, for continuous measurement. A chi-square or Fisher's exact test will be used to compare categorical variables between groups of interest. A comparison of time-to-event variable between subgroups of interest will be done with a log-rank test. Associations of variables with time-to-event outcomes will be made with Cox proportional hazard models. For baseline variables the survival clock will start at baseline; for

variables measured later, a landmark analysis will be done starting the survival clock at the time the data were obtained (and removing patients who had the event of interest before that time). We will also perform a Cox regression that treats multiple measurements of a variable as time-dependent

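### Pre-treatment and on-treatment biopsies may come from different organs, and the change-from-baseline analysis in Section 12.4 takes no account of biopsy site

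*Combined protocol and SAP*

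**What the plan says.** Section 4.2, criterion 4, sets the baseline sample: "Agree to undergo a biopsy of at least one metastatic site or primary prostate prior to beginning therapy". It adds an alternative: "Adequate archival metastatic tissue can be used if available in lieu of a biopsy". Criterion 5 sets the second sample in matching terms: "Agree to undergo a biopsy of at least one metastatic site or primary prostate after 3 weeks of therapy". On agreement between the two, criterion 5 says only "Re-biopsy of same pre-treatment biopsy soft tissue site especially liver metastases is preferred", and the exploratory objectives in Section 1 treat the same site as an ideal: "tumor immune microenvironment response through on-treatment biopsy, ideally of same pre-treatment site, and collection of plasma for analysis". A bone baseline followed by a liver, node or prostate sample is therefore permitted.

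Section 12.4 lists IHC scores for the drug's targets, immune infiltrate scores, sequencing and RNA-Seq. For change from baseline it names "either a paired t-test or Wilcoxon signed rank test for continuous measures". Ordinal variables have their own rule: each change is classed as positive, negative or none, and the proportions are analyzed. Neither rule mentions biopsy site. The false discovery rate procedure covers multiplicity in the DNA and RNA data, which is a separate matter.

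Section 2.1 says that MET is expressed in primary and metastatic disease, "with evidence for higher levels of expression in bone metastases compared to lymph node metastases or primary tumors".

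**The concern.** A paired test removes differences between patients only when both halves of the pair sample the same thing. If the first sample is bone and the second is a lymph node, the within-patient difference holds both the drug effect and the organ difference. With no control arm and at most 30 pairs, nothing else in the design separates the two.

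For MET, the protocol's own background gives a reason to expect an organ difference. Other tissue markers may have one, but the documents do not say so. The ordinal rule is exposed in the same way: a bone-to-node pair can be classed as a negative change with no drug effect.

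At stake is the reading of a biopsy asked of every patient. A reported change could be partly an organ difference, or a real change could be masked by one.

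**Working it through.** The plan states no alpha, power, SD or mismatch share for these tests, so there is no figure of its own to reproduce. What follows is illustrative.

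**Inputs**
- From the documents: at most 30 pairs (Section 12.2); paired t-test or signed-rank test (Section 12.4); MET higher in bone than in node or primary, with no size given (Section 2.1).
- Assumed: 25 usable pairs; two-sided 5%; same-site paired difference with SD 1; mismatch share *p* of 10% to 40%; site shift δ = 1 SD in mismatched pairs.

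**Case A: all shifts in one direction, no drug effect**

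Bias in the mean change = *p* × δ. The variance of a difference is 1 + *p*(1 − *p*)δ². The standardized bias is √25 × *p*δ / √(1 + *p*(1 − *p*)δ²).

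| *p* | Bias (SD) | Standardized bias | False positives, normal approximation | False positives, signed-rank simulation |
|---|---|---|---|---|
| 10% | 0.10 | 0.50/√1.09 = 0.48 | 8% | about 7% |
| 20% | 0.20 | 1.00/√1.16 = 0.93 | 15% | 14% |
| 30% | 0.30 | 1.50/√1.21 = 1.36 | 28% | 24% |
| 40% | 0.40 | 2.00/√1.24 = 1.80 | 43% | 37% |

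The approximation runs a little high, and the simulated figures are the ones to use. With δ = 0.5 the simulated rates at 20%, 30% and 40% are about 7%, 10% and 15%. A separate simulation of the paired t-test with 30 pairs and δ = 1 gives about 16% at 20% mismatch and 30% at 30%. Over 10% to 50% mismatch and shifts of 0.5 to 1.5 SD, that simulation runs from about 6% to 89%, so the result depends almost entirely on the assumptions.

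If a one-way 1-SD shift opposes a true 0.6-SD drug effect, power falls from about 80% with all pairs matched to about 42%, 25% and 13% at 20%, 30% and 40% mismatch.

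**Case B: direction of shift random**

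The expected bias is zero and the false-positive rate stays near 5%. The variance rises to 1 + *p*δ². Power for a true 0.6-SD effect, 25 pairs, δ = 1, by simulation:

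| *p* | All pairs | Same-site pairs only |
|---|---|---|
| 20% | 73% | 68% |
| 30% | 70% | 63% |
| 40% | 67% | 56% |

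The ordering follows from the standardized effects. All pairs give 5 × 0.6/√(1 + *p*) = 3/√(1 + *p*), and same-site pairs give 3√(1 − *p*). Since (1 + *p*)(1 − *p*) = 1 − *p*² < 1, the all-pairs value is larger.

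**Low end.** Section 12.1 plans up to 28 patients with liver metastases, out of 30 in Section 12.2. If all 28 gave liver-liver pairs and the other two were mismatched, *p* = 2/30 = 7%. The simulated false-positive rate at 7% mismatch under Case A is about 6%.

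None of these rates describe the ordinal summary, which was not simulated.

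**The case against.** Several stronger readings are tempting, and the documents do not support them.

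- **That criterion 5 moves the second biopsy from bone towards soft tissue, so the shift runs one way.** The sentence prefers going back to the same soft-tissue site. It asks for a match when the baseline is soft tissue and is silent when the baseline is bone. A consistent direction is possible but not established, and every inflated false-positive rate above depends on one.
- **That MET by IHC goes through the paired t-test or signed-rank test.** Section 12.4 reserves those tests for continuous measures. Section 4.4 grades IHC as 3+, so IHC scores probably fall under the ordinal rule. Site can still distort that summary, but the simulated rates do not measure by how much.
- **That any bone-to-soft-tissue pair shows a MET change without drug.** Section 2.1 reports an average tendency, "higher levels of expression in bone metastases compared to lymph node metastases or primary tumors". It gives no size and no liver figure. The documents state no site difference for immune infiltrate.
- **That same-site pairs should replace all pairs.** Case B shows that this would cost power if mismatch is random in direction.

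Two further objections have weight. If enrolment is mostly liver disease and the preference is followed, mismatch may be low and the effect small. Biopsy site may also already be recorded in pathology reports or under the Lab Manual named in Section 9.1, which is not available here. What remains is that mismatched pairs are allowed and Section 12.4 does not say how they are analyzed. Section 9 asks for cores from a single site, but that concerns one biopsy occasion and not agreement between the two.

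**Conclusion.** The gap is real, and its size is unknown. Different-organ pairs are permitted, the protocol itself reports a site difference in one main target, and neither the continuous nor the ordinal analysis of change deals with site. Under a one-way 1-SD shift with 25 pairs, the signed-rank false-positive rate is about 7% at 10% mismatch and 14% to 37% at 20% to 40%. With random direction there is no bias and a modest loss of power. The shift, its direction and the mismatch share are all assumptions. A reader might infer that the tissue results are bound to be biased; the documents support only that they could be, and that the plan as written would not show it. The analyses are exploratory, and rPFS, tumor response, PSA decline and OS are untouched. This is a point to consider, not a condition for the trial to proceed.

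**What to change.** Add to Section 12.4:

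1. Organ and lesion are recorded for both biopsies, archival baseline tissue included, and kept as analysis variables.
2. Change from baseline in tissue markers (IHC, infiltrate, RNA) is analyzed in pairs from the same lesion, or at least the same organ type. This covers both the continuous tests and the ordinal summary.
3. That analysis is reported beside the all-pairs analysis, with the number of mismatched pairs and their organ combinations.
4. A drug effect on a tissue marker is claimed only if the same-site pairs show a consistent direction and size.

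The cost is a few sentences and, at most, two data fields; no new procedure is needed. The same-site analysis has fewer pairs. Under the assumptions above, its power for a 0.6-SD effect is about 68% to 56% at 20% to 40% mismatch, against 73% to 67% for all pairs if mismatch is random in direction. Reporting both keeps the all-pairs result available, and fixing the pair sets in advance stops the choice being made after the results are seen.

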## 1.1 Schema

## 1.2 Study Objectives

To determine the anti-tumor effects of cabozantinib in patients with mCRPC who have received prior anti-androgen therapy and harbor known amplifications or activating mutations in gene targets of cabozantinib or who have liver metastases.

### 1.2.1 Primary Objectives

To assess the radiographic response proportion of cabozantinib in patients with metastatic CRPC who have progressed on an androgen receptor signaling inhibitor whose tumor possess a molecular abnormality that is targeted by cabozantinib or who have liver metastases.

### 1.2.2 Secondary Objectives

- To assess PSA decline by PCWG3 criteria
- To measure overall survival (OS)

### 1.2.3 Exploratory Objectives

- To evaluate for and measure changes in targeted altered genes found in cell free DNA at baseline, in response to treatment, and at the time of disease progression.
- To explore the effects of cabozantinib on tumor immune microenvironment response through on-treatment biopsy and collection of plasma for analysis.
- To explore any relationship between baseline and on-treatment tumor genomic abnormalities (such as mutations, translocations, messenger ribonucleic acid [mRNA], protein expression and localization) with any observed antitumor activity.

## 2. BACKGROUND

### 2.1 Prostate Cancer

Prostate cancer (PC) is the most common non-skin cancer diagnosed in men in the United States and the second most common cause of cancer-related mortality [1]. Despite advances in diagnostic technology and treatment strategies, up to 40% of patients treated with primary therapy with curative intent will experience disease progression [2]. The standard of care for men who develop metastatic PC has evolved over the past few years. Results of three phase III studies, CHAARTED, STAMPEDE and LATITUDE, have shown that men with newly diagnosed metastatic PC benefit from early use of docetaxel chemotherapy or abiraterone acetate plus prednisone in conjunction with androgen deprivation therapy (ADT) [3-6]. Subsequent therapies following disease progression in men with CRPC include abiraterone or Enzalutamide in men who have received ADT plus docetaxel, or Enzalutamide or docetaxel in men who have progressed on ADT plus abiraterone. Men who progress on ADT alone and become castrate-resistant are generally offered abiraterone or Enzalutamide as second line therapy. Other approved therapies for men with CRPC include docetaxel chemotherapy, Sipuleucel-T, Radium-223 and cabazitaxel chemotherapy [7-9]. Nevertheless, nearly all men with CRPC will eventually progress [2, 10]. Deaths from PC are typically the result of mCRPC, and historically the median survival for men with mCRPC has been less than two years [11]. With the exception of rare subpopulations with homologous recombination repair deficiency or mismatch repair defects that may respond preferentially to PARP inhibitors or immune checkpoint blockade, respectively, alternative targeted therapies for prostate cancer are lacking [12-14].

#### *MET and VEGFR2 signaling in prostate cancer*

Beyond AR signaling, PC growth can be affected through targeting the MET and VEGFR2 signaling

pathways. The receptor tyrosine kinase MET plays important roles in cell motility, proliferation, and survival, and has been shown to be a key factor in tumor angiogenesis, invasiveness, and metastasis. Prominent expression of MET has been observed in primary and metastatic PCs [15, 16] with evidence for higher levels of expression in bone metastases compared to lymph node metastases or primary tumors [17, 18]. Overexpression of hepatocyte growth factor (HGF), the ligand for MET, has also been observed in PC [19], and increased plasma levels of HGF in CRPC are associated with decreased overall survival [20].

Data from preclinical studies suggest that both HGF and MET are regulated by the AR signaling pathway in prostatic tissue [15, 21, 22]. MET expression increases substantially in androgen-sensitive tumor cells after androgen withdrawal [15, 21, 22]. Administration of a MET kinase inhibitor after castration reduced tumor cell proliferation in a preclinical model of CRPC [21]. These observations indicate that upregulation of MET signaling may be associated with and contribute to the emergence of resistance to androgen suppression in PC.

Vascular endothelial growth factor (VEGF) and its receptors are key mediators in the process of tumor neoangiogenesis, invasion, and metastasis [23]. In PC, elevated VEGF in either plasma or urine is associated with shorter overall survival [24, 25]. VEGF may also play a role in activating the MET pathway in tumor cells by binding to neuropilin-1, which is frequently upregulated in PC and appears to activate MET in a co-receptor complex [18]. Agents targeting the VEGF signaling pathway have demonstrated activity in some patients with CRPC [26].

